6.6.2 SECONDARY ENDPOINTS

The secondary endpoint will be the change at the end of treatment or early termination visit from baseline in the Montreal Cognitive Assessment (MoCA) score.

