4.1 Primary endpoint

4.1.1 Objectives:

The primary objective of this study will be to evaluate the safety and feasibility of time varying caloric vestibular stimulation (tvCVS), delivered with a solid-state TNM™ Device, in people with mild/moderate Parkinson's disease dementia (PDD).

4.1.2 Endpoint:

The primary endpoints of this study are the following:

- Safety will be evaluated by evaluating whether tvCVS is associated with a worsening of PD signs and symptoms according to The International Parkinson and Movement Disorder Society Unified Parkinson's Disease Rating Scale Total Score: composite score of Parts I, II and III.

Adverse events will also be monitored.

- Feasibility:
 - Retention rate or the percent of participants that complete assessments required for analysis of the secondary endpoint:
 - High retention: >90%
 - Moderate retention: 60-90 %
 - Low retention:< 60 %
 - Treatment adherence rate during the 12-week treatment period:
 - High adherence: >84%
 - Moderate adherence: 55-84 %
 - Low adherence: < 55 %

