4.2 Secondary endpoints

4.2.1 Objectives:

The secondary objective of this trial is to assess the effects of tvCVS on cognition in people with mild/moderate PDD.

4.2.2 Endpoints:

The secondary endpoint will be the change in the Montreal Cognitive Assessment (MoCA) between the baseline and end of treatment visit (Day 84) after 12 weeks of treatment. 3 different versions of the MoCA (8.1, 8.2, and 8.3) will be used to avoid learning effects, and the ordering of the version for a given participant will be randomized. The MoCA is a rapid screening instrument for detecting cognitive dysfunction and dementia in patients with neurologic disorders including PD.

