- NAB Visual Discrimination
- Oral SDMT
- HVLT-R (Trial 4 and Recognition)
- D-KEFS Category Fluency (skip Condition 1-Letter Fluency for this study)
- D-KEFS Fluency Switching

If the CCB could not be performed at Day 0 or Day 3, then no further attempts should occur and the participant is not considered as part of the sub-study.

Virtual visits will be performed, as necessary, using the site's standard of care telemedicine platform.

Early Treatment Period Visit 2 - day 6 (+/- 3 days) – as needed: *This in-clinic visit may be completed virtually at the participant and study partner's request. This visit only needs to be completed if the study participant and study partner required retraining on use of the study device at the Early Treatment Period Visit 1 - day 3.* The participant (with the assistance of the study partner as appropriate) should complete a treatment administration at the study site to demonstrate to study staff an understanding of how to use the study Device. If participants and their study partner meet the criteria specified in the Treatment Administration Verification Form, the participant will then take the study Device home, treat once more for the day, and commence again with twice daily treatments. If participants and their care partners do not meet the criteria specified in the Treatment Administration Verification Form, the participant will **be withdrawn from the study.**

Phone contacts: (Days 14, 28, +/- 3 day)

During phone calls scheduled every 2 weeks, study staff will review concomitant medications, potential adverse events, potential issues impacting Device treatment adherence and any other issues with the study participant (and study partner, as appropriate). Care should be taken to not over-engage or impact feasibility of protocol adherence with reminders or contact outside of the protocol-defined visits/calls.

Interim treatment Visit: (Day 42 +/- 5 days)

The visit activities should be performed per the SOE. Assessments followed by (SP) should be completed by the study care partner only.

- Confirmation of timing of last DRT dose

SHARPEN, V3.0 -- CONFIDENTIAL

Clinician version – not for patient use

- MoCA v8.2 (on-state)

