8.2 Lost to Follow-Up

8.2.1 Withdrawal Criteria

Participants must be withdrawn from the clinical trial if any of the following events occur:

- the participant is significantly non-adherent to the requirements of the protocol (principal investigator & Sponsor decision, of note requirements relate to participation and completion of activities during study visits and do not include adherence of treatments with the study device),
- the participant develops an illness or condition that would interfere with his/her continued participation,
- the participant withdraws his/her consent,
- the participant's study partner withdraws his/her consent and no replacement can be found

Clinician version – not for patient use

- the principal investigator feels that it is the participant’s best interest to be withdrawn,
- the participant and/or their study partner is unable to demonstrate device use at the required visits
- SNS discontinues the study or has achieved the targeted enrollment,

If the participant is discontinued from the participation in the study for any reason, the principal investigator must make every effort to perform all evaluations for the final visit, even virtually, if necessary, collect the device from the participant and document the reasons for discontinuation. If the participant withdraws from the study due to an adverse event that is potentially related to use of the device, the study staff should continue to follow up with the participant at regular intervals, and at least every two weeks until the AE resolves or until the participant withdraws consent for the follow-up procedure.

If a participant’s study partner withdraws their consent from the study, a new study partner who meets the criteria may be identified and consented to the study. If a suitable study partner cannot be found, the participant will be withdrawn from the study.

Participants that withdraw early will be excluded from the per protocol analysis.

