1. INTRODUCTION

This document describes the statistical analysis plan (SAP) for SNS-PD-004, the multicenter single arm safety and feasibility trial described in the protocol Simple, Home-use neurostimulAtion tReatment for Parkinson's disease dEmeNtia (Brief title: SHARPEN). This analysis plan is meant to supplement the study protocol. Any deviations from this analysis plan will be described in the clinical study report.

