2.2. STUDY ENDPOINTS

Primary Endpoints

• Safety will be evaluated by determining whether tvCVS is associated with a worsening of PD signs and symptoms according to The International Parkinson and Movement Disorder Society Unified Parkinson's Disease Rating Scale (MDS-UPDRS) combined measure of Parts I, II, and III (Goetz, Tilley et al. 2008). This endpoint will evaluate the change in the summed score of MDS-UPDRS Parts I, II and III at the end of the treatment period (day 84), which is defined based on the change relative to baseline (day 0) score.

Adverse events will also be monitored.

- Feasibility will be defined by evaluating both retention rate and treatment adherence rate. Specifically,
 - Retention rate will be defined by the percentage of participants that complete assessments required for analysis of the secondary endpoint:
 - High retention: >90%
 - Moderate retention: 60-90%
 - Low retention: < 60%
 - Treatment adherence rate for each participant will be defined as the percentage of twice-daily treatments with the neuromodulation device completed during the 12-week treatment period:
 - High adherence: >84%
 - Moderate adherence: 55-84%
 - Low adherence: < 55%

Secondary endpoint: The secondary endpoint will evaluate change in the Montreal Cognitive Assessment (MoCA).

Exploratory endpoints: The following outcome measures will be used:

- The Zarit Burden Interview of Caregivers (ZBI)
- The Patient Global Impression of Improvement (PGI-I)
- The Neuropsychiatric Inventory Questionnaire (NPI-Q)
- The Modified Schwab and England Activities of Daily Living Scale (S & E)
- A customized cognitive battery (CCB) which will assess the following functions:
 - Memory
 - Hopkins Verbal Learning Test-Revised (total learning)
 - Hopkins Verbal Learning Test-Revised (delayed recall)
 - Hopkins Verbal Learning Test-Revised (recognition discrimination)
 - o Visuospatial
 - Neuropsychological Assessment Battery Visual Discrimination
 - o Language
 - Delis-Kaplan Executive Function System Semantic Fluency
 - Attention
 - Neuropsychological Assessment Battery Digits Forward
 - Hopkins Verbal Learning Test-Revised (Trial 1)
 - Processing speed
 - Oral Symbol Digit Modality
 - Executive Function
 - Delis-Kaplan Executive Function System Semantic Fluency Switching
 - Neuropsychological Assessment Battery Digits Backward

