6.6.1 PRIMARY ENDPOINTS

(Safety) MDS-UPDRS Parts I, II & III summed score: Changes will be considered to be clinically meaningful worsening if the median difference meets or exceeds the previously established MCID (+5.2 points for clinical worsening) (Makkos, Kovacs et al. 2018). Two-sided, 90% confidence intervals for the combined MDS-UPDRS Parts I, II, and III scores at baseline and the end of treatment period will be constructed. If the median difference (baseline- end of treatment) is less than 5.2 and the confidence interval of the difference (baseline – end of treatment) contains 5.2, then the no clinically meaningful worsening.

(Feasibility)

- **Retention rate** will be defined by the percentage of participants that complete assessments required for analysis of the secondary endpoint:
 - High retention: >90%
 - Moderate retention: 60-90 %
 - Low retention: < 60 %
- **Treatment adherence** rate for each participant will be defined as the percentage of twice-daily treatments with the neuromodulation device completed during the 12-week treatment period:
 - High adherence: >84%
 - Moderate adherence: 55-84 %
 - Low adherence: < 55 %
 - Treatment adherence is captured by the study device and will be reported summarized with minimum, 1Q, median, 3Q, and maximum values. Treatment adherence of \geq 70% is required for inclusion in the Per Protocol cohort.

Adverse Events (AEs): Participants will be assessed for AEs every two weeks at minimum (either at study visits or during phone calls). For each group, the AEs will be summarized with frequency and percentage by preferred (PT) term, with all participants in that treatment group as the denominator. Classification will utilize MedDRA System Organ

Class (SOC) based on MedDRA® Version 26.0 or other terminology/classification common to Parkinson's disease (e.g., falls, freezing of gait, etc.). AE incidence will be summarized by both severity and causal relationship to Device treatment (as determined by the blinded Principal Investigator or designated study personnel). AEs deemed to be of "possible" or "probable" relationship or "related" to the Device will also be considered as device related. Additionally, the number of events and number of device-related events per person will be reported as a distribution.

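### SAP 6.6.2 lets an early leaver with an exit MoCA count as retained in a primary feasibility endpoint; protocol 4.2.2, which fixes the MoCA at Day 84, does not

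*SAP*

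**What the plan says.** **Retention.** SAP 6.6.1 says the rate "will be defined by the percentage of participants that complete assessments required for analysis of the secondary endpoint". SAP 2.2 and protocol 4.1.2 define it the same way. The bands are High above 90%, Moderate 60-90% and Low below 60%. None of the three places gives a visit or day, so the timing of retention comes entirely from the secondary endpoint.

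**Secondary endpoint.** Protocol 4.2.2 takes the MoCA change "between the baseline and end of treatment visit (Day 84) after 12 weeks of treatment". SAP 6.6.2 takes "the change at the end of treatment or early termination visit from baseline in the Montreal Cognitive Assessment".

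**Exit assessments.** Under protocol 8.2.1, when a participant is discontinued for any reason, "the principal investigator must make every effort to perform all evaluations for the final visit". Protocol 5.1.1 and the schedule of events (protocol Appendix 1.0) list one set of procedures, including the MoCA, for the end of treatment and early termination visits.

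**Related wording.** The per-protocol definition in SAP 6.1 requires the regularly scheduled Day 84 visit. The 75% Go criterion is worded in protocol 10.1 as completing the end of treatment visit. SAP 4 words it through the secondary-endpoint assessments and then explains it as at least 9 participants with a MoCA at the end-of-treatment visit.

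**The concern.** A primary endpoint that borrows its timing from another endpoint inherits any disagreement about that other endpoint. Here the two documents disagree on whether an early-termination MoCA belongs to the secondary endpoint, so the same data can give two retention rates.

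The case is foreseeable. At the Day 6 (+/- 3 days) device check in protocol 5.1.1, a participant is withdrawn "If participants and their care partners do not meet the criteria specified in the Treatment Administration Verification Form". That person was treated at the baseline visit and so belongs to the intention-to-treat (ITT) population of SAP 6.1. If the final-visit evaluations sought by protocol 8.2.1 are obtained, there is an exit MoCA after about a week of treatment. SAP 6.6.2 allows that to count as completing the required assessment; protocol 4.2.2 does not.

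At stake is the reported High, Moderate or Low retention category. If the rule is chosen once the data are known, the choice is discretionary, and the SAP rule can only match or exceed the protocol's rate.

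**Working it through.** **Inputs.** The number treated is 12 (SAP 2; protocol 10.1). The bands are those of SAP 6.6.1. Let m be the number of treated participants with no Day 84 MoCA, and e the number of those m who give an exit MoCA.

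**The plan's own figure.** 75% of 12 is 0.75 x 12 = 9, which matches SAP 4 and protocol 10.1. It also shows that the plan counts completers out of all 12 treated, so that denominator is used below.

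**Formulas.**
- Protocol 4.2.2 rate = (12 - m)/12.
- SAP 6.6.2 rate = (12 - m + e)/12.
- The difference is e/12, or 8.3 percentage points per exit MoCA. It is never negative.

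**Bands at n = 12.**
- High: 11/12 (91.7%) or 12/12 (100%).
- Moderate: 8/12 (66.7%), 9/12 (75.0%) or 10/12 (83.3%).
- Low: 7/12 (58.3%) or fewer.

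**Fewest exit MoCAs that change the category.**

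| m | Day 84 rate | e needed | SAP 6.6.2 rate | Category |
|---|---|---|---|---|
| 1 | 11/12 = 91.7% | none possible | up to 100% | High either way |
| 2 | 10/12 = 83.3% | 1 | 11/12 = 91.7% | Moderate to High |
| 3 | 9/12 = 75.0% | 2 | 11/12 = 91.7% | Moderate to High |
| 4 | 8/12 = 66.7% | 3 | 11/12 = 91.7% | Moderate to High |
| 5 | 7/12 = 58.3% | 1 | 8/12 = 66.7% | Low to Moderate |

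For m up to 5, a single exit MoCA changes the category when exactly 2 or exactly 5 participants lack the Day 84 MoCA. Other cases need more than one, or cannot change.

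**What cannot be calculated.** The chance of a changed category needs a rate of missing Day 84 and a rate of exit MoCAs among those who miss it. The documents give neither, so no probability is offered.

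**Boundary case.** Day 84 carries a +/- 5 day window, and protocol 5.2 allows up to 10 additional days for illness or injury. Someone who leaves inside the window and gives a MoCA would count on either reading.

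**The case against.** The strongest reply is that the documents already point to Day 84. The SAP says of itself: "This analysis plan is meant to supplement the study protocol". Protocol 4.1.2 read with 4.2.2 gives Day 84. SAP 4 uses the retention phrase and explains it as the MoCA at the end-of-treatment visit. Protocol 5.1.1, protocol 5.4 and SAP 6.6.2 itself all name early termination as an alternative to end of treatment, so where SAP 4 names only the latter it presumably means only that. This largely stands: Day 84 is the better reading, and SAP 6.6.2 is the passage out of line. It does not remove the conflict, because SAP 6.6.2 is where the SAP defines the endpoint that retention depends on, and it expressly admits early termination. An analyst who follows it gets the higher count.

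A second reply is that retention may be meant as completion of assessments, since adherence measures treatment separately; counting an exit MoCA would then be intended. That is possible, and the synopsis and SAP 2.2 give the MoCA change no time point. But it contradicts protocol 4.2.2 and would have to be stated.

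Two stronger readings are tempting, and the documents support neither:
- **The Go decision is compromised.** A reader might note that one exit MoCA turns 8/12 into 9/12, the 75% threshold. But protocol 10.1 words that criterion as completing the end of treatment visit, and both documents explain it as the end-of-treatment MoCA.
- **Dropout would be hidden.** It would not. SAP 6.3 summarises follow-up duration and discontinuations with reasons, SAP 6.6.1 reports adherence, and the per-protocol population in SAP 6.1 excludes anyone without the scheduled Day 84 visit.

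**Conclusion.** The point holds, confined to the retention category. A stated SAP rule can give a more favourable primary feasibility result than the protocol's rule on the same data, and one participant is enough in two configurations: 10 or 7 of 12 with a Day 84 MoCA. The effect arises only if someone leaves before the Day 84 window and gives an exit MoCA; how likely that is cannot be judged from the documents. The calculation assumes exactly 12 treated participants, all in the denominator. The label drives no test or stopping rule, and the attrition stays visible elsewhere. It should be fixed before analysis because it concerns a named primary endpoint and the remedy is simple.

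**What to change.** In SAP 2.2 and 6.6.1, define retention without reference to 6.6.2: the share of all treated (ITT) participants with a MoCA at the regularly scheduled Day 84 visit, within the protocol windows including the 10-day extension in protocol 5.2. State that early termination visits do not count as retained. SAP 6.1 already has suitable wording for the scheduled visit.

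Reconcile SAP 6.6.2 with protocol 4.2.2, and report Day 84 and early-termination MoCAs separately. Which of them forms the main MoCA analysis can remain the sponsor's choice, provided both documents say the same.

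**Cost.** No new data are needed. Reported retention may be less favourable. Reconciling the two sections means a wording change in one document: adopting Day 84 narrows the SAP's MoCA endpoint, while keeping early termination in it means amending the protocol.

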6.6.3 EXPLORATORY ENDPOINTS

These exploratory endpoints have been added to identify outcome measures to utilize in future trials. Mean or median change with corresponding 95% confidence intervals and p values will be provided. No adjustments will be made to address a multiplicity of endpoints. Only participants who have baseline and post-treatment data collected for the exploratory endpoints will be included in these efficacy analyses.

Exploratory outcomes will evaluate the change in the following measures:

- The Zarit Burden Interview of Caregivers (ZBI)
- The Patient Global Impression of Improvement (PGI-I): The Patient Global Impression-Improvement a patient determined scale to assess how much their illness has improved or worsened relative to a baseline state at the beginning of the intervention (starting with the RCT). Scoring: 1 = very much better, 2 = much better, 3 = a little better, 4 = no change, 5 = a little worse, 6 = much worse, 7 = very much worse. For ease of interpretation, the PGI-I score will be converted by the following formula: Converted PGI-I = 4 PGI-I. Thus a 0 corresponds to no change, higher magnitude positive values correspond to greater improvements and higher magnitude negative scores correspond to increased worsening. If the lower limit of the 95% CI is positive, this would indicate improvement.
- The Neuropsychiatric Inventory Questionnaire (NPI-Q)
- The Modified Schwab and England Activities of Daily Living Scale (S & E)
- A customized cognitive battery (CCB) which will assess the following functions
 - o Memory
 - Hopkins Verbal Learning Test-Revised (total learning)
 - Hopkins Verbal Learning Test-Revised (delayed recall)

- Hopkins Verbal Learning Test-Revised (recognition discrimination)
- Visuospatial
 - Neuropsychological Assessment Battery Visual Discrimination
- Language
 - Delis-Kaplan Executive Function System Semantic Fluency
- o Attention
 - Neuropsychological Assessment Battery Digits Forward
 - Hopkins Verbal Learning Test-Revised (Trial 1)
- Processing speed
 - Oral Symbol Digit Modality
- Executive Function
 - Delis-Kaplan Executive Function System Semantic Fluency Switching
 - Neuropsychological Assessment Battery Digits Backward
- Analysis of the customized cognitive battery will be described in a supplemental statistical analysis plan and will not be included in the main statistical analyses for this study.

